TITLE: Evaluation of two different methods of teaching self-management strategies to patients with symptomatic knee osteoarthritis

NCT: 03245463

DOCUMENT DATE: July 25, 2017

**Title:** Evaluation of two different methods of teaching self-management strategies to patients with symptomatic knee osteoarthritis

**Principal Investigator:** [name], MD

**Condition or Intervention to be studied:** The condition being studied is self-management education for patients who have symptomatic knee osteoarthritis (OA) and are scheduled for a hyaluronic acid (HA) injection.

**Research questions/specific aims:** This is a pilot study to evaluate two different teaching methods of self-management education to patients receiving an HA injection for symptomatic knee OA. The main goal is to see if the study can be feasibly conducted. Feasibility will be determined by availability of the fellows/residents to administer the assigned teaching method to the potential patient (if they are unavailable 70% of the time, then the study will be deemed to be not feasible). The other goals are to obtain information on the following:

1. Patient satisfaction with their assigned teaching methods.
2. Education methods that are preferred by patients.
3. Provider (fellows and residents) satisfaction with their assigned teaching methods.
4. Teaching methods that are preferred by fellows and residents.

**Hypothesis:** We hypothesize that the study can be feasibly conducted, and that patient satisfaction with assigned teaching method 2 (education handout + 5-minute explanation) will be higher than patient satisfaction with assigned teaching method A (educational handout only, no explanation).

**Primary outcome:**

1. Patient satisfaction with their assigned teaching method (0-10 scale; 0=not satisfied; 10=most satisfied) – assessed at 1 and 3 months post-injection
2. Provider (fellow, resident) satisfaction with their assigned teaching method (0-10 scale; 0=not satisfied; 10=most satisfied) – assessed at 1 and 3 months post-injection

**Secondary outcomes:**

1. Patient preference regarding teaching method – assessed at 1 and 3 months post-injection
2. Provider preference regarding teaching method – assessed at 1 month post-injection
3. Quality of education on post-injection care – assessed at 1 and 3 months post-injection
4. PROMIS-10 – assessed at 1 and 3 months post-injection

**Background:** Symptomatic knee OA is a condition that is characterized by frequent pain to the joint and affects approximately 10 million adults in the United States. By age 60, the lifetime risk of being diagnosed with symptomatic knee OA is 9.29%. Increases in symptomatic knee OA pain have been associated with higher BMI, greater comorbidity, and lower level of education. For patients who do not want to have surgery, treatment options include pharmacologic injections, physical therapy, and medications, with the goal of relieving symptoms, improving quality of life, and restoring physical function. Regardless of treatment type, achieving the abovementioned goals requires self-management.

In 2003, the EULAR consensus stated that patient education should be provided to patients with symptomatic knee OA to help them understand and self-manage their condition.

However, there is a lack of consensus on the best teaching methods to educate our patients with symptomatic knee OA on self-management strategies. Different physician practices within a department or across different departments utilize different strategies to accomplish these goals. Many provide direct doctor-to-patient teaching that may occur during an office visit (one-on-one) or with a small group. Others may rely on educational handouts or other forms of individual education that are given to patients. Some utilize both methods of teaching, and others rely on physical therapists to provide this education to their patients as part of their physical therapy program. There are many other teaching methods, and variations of previous methods also exist.

Numerous studies on different patient education methods in various patient populations have been conducted. Both the content and delivery of education materials are essential to having a successful method. Whether one method is effective depends largely on the patient's self-efficacy, ability to understand the materials, and willingness to cooperate. This is especially key to having success with self-management protocols. Any stress that may result from an ineffective education tool can also adversely affect a patient's outcomes. In the general OA population, Hansson et al. demonstrated an increase in self-perceived health in patients who participated in an OA-targeted patient education program (5 group sessions) compared to patients who did not participate in the program. However, no differences in self-efficacy were observed, and patient satisfaction was not assessed. A review by Brand et al. in 2013 showed improvements in self-efficacy with regard to decreasing pain in arthritis patients receiving self-management education, although these effect sizes were very small and likely not statistically significant in some cases. Again, many of these studies did not assess patient satisfaction. Recently, the development of video-based patient education tools was tested in patients with knee osteoarthritis (both symptomatic and not), rheumatoid arthritis, and osteoporosis. The results showed increases in disease knowledge, and patients appeared to be more aware about taking their medications. Future advances in patient education are likely to incorporate multimedia tools as a way to better engage the patient.

With all this being said, studies that are focused on patient education involving self-management methods in the symptomatic knee OA population are lacking. A literature search revealed one study looking at the effects of an 8-week multimodal treatment program that improved symptoms of symptomatic knee OA. Patient education was a component of the treatment program, but whether it specifically contributed to symptom improvement is unknown. Given the degree of disability that these patients live with on a daily basis, clarifying the proper method of self-management education is important. This pilot study aims to take the first step at evaluating two different methods of teaching: one involving a written handout that's given to the patient for him/her to read at home, and one involving the same written handout that is explained to the patient by the provider. Future studies will evaluate other commonly utilized methods of teaching, as well as longer periods of follow-up.

1. Lawrence RC, et al. Estimates of the prevalence of arthritis and other rheumatic conditions in the United States, part II. *Arthritis Rheum.* 2008 Jan;58(1):26-35.
2. Losina E, et al. Lifetime risk and age of diagnosis of symptomatic knee osteoarthritis in the US. *Arthritis Care Res.* 2013 May;65(5).
3. Bastick AN, et al. Defining knee pain trajectories in early symptomatic knee osteoarthritis in primary care: 5-year results from a nationwide prospective cohort study (CHECK). *Br J Gen Pract.* 2016 Jan;66(642):e32-9.
4. Jordan KM, et al. EULAR Recommendations 2003: an evidence-based approach to the management of knee osteoarthritis: report of a task force of the standing committee for

international clinical studies including therapeutic trials (ESCISIT). *Ann Rheum Dis.* 2003 Dec;62(12):1145-55.

5. Schrieber L, et al. Patient education. *Best Prac Res Clin Rheum.* 2004;18(4):465-476.
6. Friedman AJ, et al. Effective teaching strategies and methods of delivery for patient education: a systematic review and practice guideline recommendations. *J Cancer Educ.* 2011 Mar;26(1):12-21.
7. Koehn CL, et al. Patient education and self-management of musculoskeletal diseases. *Best Prac Res Clin Rheum.* 2008;22(3):395-405.
8. Brand E, et al. Arthritis self-efficacy scale scores in knee osteoarthritis: a systematic review and meta-analysis comparing arthritis self-management education with or without exercise. *J Orthop Sports Phys Ther.* 2013 Dec;43(12):895-910.

**Inclusion criteria:**

1. Age 18+
2. Diagnosis of symptomatic knee OA
3. Scheduled for an HA injection into the knee
4. Fellow/resident is available to administer assigned teaching method

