**Exclusion criteria:**

1. Patients who are already enrolled in the study
2. Non-English speaking

**Study procedures:** Patients who have symptomatic knee OA and are coming in for an HA injection will be approached for the study. At the time of consent, patients will be told that they will be receiving educational materials, and that the study will be focusing on outcomes in patients who receive educational materials. Details related to the two teaching methods will only be revealed to the patients at the 3-month follow-up, in order to prevent any bias in their responses. The primary investigator and research assistant will be blinded to the randomization group.

Enrolled patients will be randomized to receive one of two teaching methods:

1. A written handout will be given to the patient, and the patient will be asked to read the handout at home and call back with any questions or clarifications.
2. A written handout will be given to the patient, and key information will be explained to the patient with time for questions and answers (approximately 5 min).

The written handout includes a description of knee OA, treatment options for knee OA, and instructions for the self-management of knee OA.

During the icing period post-injection, a fellow or resident will return to the exam room and administer either teaching method 1 or 2 to the patient (depending on the randomization assignment). The same written handout will be given to every patient. The explanation of key information will be standardized as much as possible to prevent against large variations in teaching methods among fellows and residents.

At 1 month following the educational handout/session, the fellows and residents will be surveyed regarding their satisfaction with the teaching method and if they would have preferred to teach the information in a different manner.

At 1 month and 3 months following the educational handout/sessions, patients will be asked the following questions:

1. On a scale of 0-10, with 0=not satisfied and 10=most satisfied, please rate your satisfaction with the education you received on the day of your injection.
2. Would you have preferred a different method of receiving education? If yes, what method?
3. Did the education you received help with the care of your osteoarthritis? If yes, please explain how it helped.
4. PROMIS-10 questionnaire (also administered at baseline, after consent)

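### Inclusion criterion 4 requires a provider to be available for the assigned method, but only enrolled patients are assigned; availability should be judged for either method before the assignment is opened

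*Combined protocol and SAP*

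**What the plan says.** Inclusion criteria, item 4 (the list appears twice in the combined document, worded identically), requires "Fellow/resident is available to administer assigned teaching method". Research questions/specific aims uses the same term for the pilot's main goal: "Feasibility will be determined by availability of the fellows/residents to administer the assigned teaching method to the potential patient". The rule attached to it is that "if they are unavailable 70% of the time, then the study will be deemed to be not feasible".

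Study procedures places allocation after enrolment: "Enrolled patients will be randomized to receive one of two teaching methods". Delivery comes later still: "During the icing period post-injection, a fellow or resident will return to the exam room and administer either teaching method 1 or 2", according to the allocation.

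The methods ask different amounts of provider time. In method 1 a handout is given and "the patient will be asked to read the handout at home and call back with any questions or clarifications". In method 2 the same handout is given and "key information will be explained to the patient with time for questions and answers (approximately 5 min".

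The principal investigator and the research assistant are to be kept blind to the group. The documents do not say who judges criterion 4 or when. The statistical analysis plan fixes 12 patients per group and describes no count of provider availability.

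**The concern.** Eligibility should be settled before anyone can know the arm. Criterion 4 refers to an assignment that, under Study procedures, does not exist until the patient is enrolled. Staff who follow the criterion literally must either open the assignment during screening or drop a patient after randomisation when nobody is free for that patient's method. In both cases the arm can influence who stays in the study.

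The arms also differ in what they demand. A provider with a minute to spare could hand over a leaflet but could not give a 5-minute explanation. Patients arriving at busy times could then be kept in the handout arm and lost from the explanation arm. The comparison at stake is patient satisfaction, which is a primary outcome and carries the study's directional hypothesis.

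A secondary matter is the source of the 70% unavailability figure. Criterion 4 removes the very patients whom that figure is meant to count, so it has to be recorded before the criterion is applied.

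**Working it through.** **Plan's own figure.** 2 groups × 12 = 24, as stated. It is a rule-of-thumb size with no power calculation, and nothing below changes it.

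**Order of events.** Criterion 4 needs the assigned method; assignment needs enrolment; enrolment needs criterion 4. The circle is in the text and does not depend on any number.

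**Exclusions by arm under the literal reading.** Let p1 and p2 be the probability that a provider is free for methods 1 and 2. The documents give neither, so the values here are assumptions. Of 12 patients assigned to each arm, 12 × p1 and 12 × p2 are kept:

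| p1 / p2 (assumed) | Kept, method 1 | Kept, method 2 |
|---|---|---|
| 90% / 90% | 10.8 | 10.8 |
| 90% / 70% | 10.8 | 8.4 |
| 90% / 50% | 10.8 | 6.0 |

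Exclusions differ only if availability differs.

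**When unequal exclusion becomes bias.** Assume that a provider free for method 2 is also free for method 1. Patients kept in arm 2 then all come from times when either method was possible. In arm 1 a share (p1 − p2)/p1 comes from times when only the handout was possible. Let d be the difference in mean satisfaction between those busy-time patients and the others. If teaching method had no effect, the expected difference, arm 2 minus arm 1, would be −d × (p1 − p2)/p1:

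- 90% / 90%: 0/0.90 = 0, so no distortion.
- 90% / 70%: 0.20/0.90 = 0.22, so −0.22 d.
- 90% / 50%: 0.40/0.90 = 0.44, so −0.44 d.

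Bias therefore needs both p1 ≠ p2 and d ≠ 0. The documents are silent on p1, p2 and the sign of d, so size and direction are unknown.

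**Where the 70% figure must come from.** Among enrolled patients, criterion 4 has already been met, so unavailability at entry is 0/24 by construction. Counted beforehand, with unavailability u and everyone with an available provider consenting, the number of potential patients needed is 24/(1 − u). At u = 10%, 30% and 50% (assumed) this is 27, 35 and 48, rounded up. At 70% it is 24/0.30 = 80, of whom 80 − 24 = 56 have no provider.

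**Effect of changing the wording.** With 1:1 assignment and the same nesting assumption, unavailability for the assigned method is 1 − (p1 + p2)/2, and for either method 1 − p2. At 50% / 50% both are 50%. At 70% / 50% they are 40% and 50%. The second is never smaller, so a threshold set for one does not carry over automatically to the other.

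**The case against.** The strongest reply is that the authors meant availability for whichever method is then assigned. Study procedures randomises only enrolled patients, and the delivery sentence makes the method follow from the allocation. Two study staff are also blinded, which would limit arm-aware exclusion if they do the screening. This reading is plausible, perhaps the likelier one. But neither criterion 4 nor the aims says it, the circular wording occurs in both places, and a blinded screener could not apply the criterion as written. The reply lowers the probability of harm and shows that the remedy is short; it does not remove the ambiguity.

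Four stronger readings may tempt a reader, and the documents do not support them.

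- *Randomisation is shown to be broken.* It is not. Bias requires the literal reading, unequal availability, and busy-time patients who would rate differently. No passage establishes the last two.
- *The 70% rule can never be met.* That holds only if enrolled patients are the denominator. The aims name the potential patient, so the rule is workable; what is missing is a planned record.
- *The wording already changes the feasibility verdict.* One can choose assumed availabilities, such as 90% and 30%, that give 40% unavailability for the assigned method and 70% for either method. The change then comes from redefining the measure with invented inputs, and it lands exactly on the cut-off.
- *Undelivered sessions need a set missing-data rule.* The plan does not say what happens if no provider returns, although the patient item reads "please rate your satisfaction with the education you received on the day of your injection". This is a separate gap. Setting such ratings to missing could itself bring back arm-dependent loss, so no rule is prescribed here.

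That this is a small, mainly descriptive pilot argues for a light remedy. It does not argue for leaving an eligibility criterion that refers to the arm.

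**Conclusion.** The point holds as a defect of wording with a possible selection bias, not a demonstrated one. As written, criterion 4 can be applied only with the arm known, and because method 2 needs about 5 minutes more provider time, exclusions could differ by arm. The size and direction of any effect on satisfaction cannot be estimated from the documents; the figures above are illustrations under assumed availabilities, nested availability and, where stated, full consent. The need to record availability before criterion 4 is applied is a supporting detail that follows from the 0/24 result. The point should be fixed because the protection is specific and cheap. Confidence is medium, since the benign reading may be what was intended.

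**What to change.** 1. Reword criterion 4 in both copies to: *a fellow/resident is available to deliver either of the two methods, whichever is then assigned*. State that this is judged and recorded as yes or no before the assignment is opened, and by whom.
2. Keep every randomised patient in the assigned arm. Report undelivered sessions by arm.
3. Take the 70% unavailability figure from the same record: patients without an available provider, divided by all otherwise-eligible potential patients, counted before criterion 4 is applied. Align the sentence in the aims with this measure, and have the sponsor confirm that the 70% threshold applies to availability for either method.

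The cost is a change of wording and an anonymous screening tally; the enrolment target stays 24. The criterion becomes stricter, so somewhat more patients may need to be screened. How many more depends on the gap between p1 and p2. Under the assumptions above, equal availability of 50% leaves the number at 24/0.50 = 48. Availability of 70% and 50% moves it from 24/0.60 = 40 to 24/0.50 = 48. A wide gap of 90% and 30% would move it from 24/0.60 = 40 to 24/0.30 = 80.

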**Exclusion criteria:**

1. Patients who are already enrolled in the study
2. Non-English speaking

**Study procedures:** Patients who have symptomatic knee OA and are coming in for an HA injection will be approached for the study. At the time of consent, patients will be told that they will be receiving educational materials, and that the study will be focusing on outcomes in patients who receive educational materials. Details related to the two teaching methods will only be revealed to the patients at the 3-month follow-up, in order to prevent any bias in their responses. The primary investigator and research assistant will be blinded to the randomization group.

Enrolled patients will be randomized to receive one of two teaching methods:

1. A written handout will be given to the patient, and the patient will be asked to read the handout at home and call back with any questions or clarifications.
2. A written handout will be given to the patient, and key information will be explained to the patient with time for questions and answers (approximately 5 min).

The written handout includes a description of knee OA, treatment options for knee OA, and instructions for the self-management of knee OA.

During the icing period post-injection, a fellow or resident will return to the exam room and administer either teaching method 1 or 2 to the patient (depending on the randomization assignment). The same written handout will be given to every patient. The explanation of key information will be standardized as much as possible to prevent against large variations in teaching methods among fellows and residents.

At 1 month following the educational handout/session, the fellows and residents will be surveyed regarding their satisfaction with the teaching method and if they would have preferred to teach the information in a different manner.

At 1 month and 3 months following the educational handout/sessions, patients will be asked the following questions:

1. On a scale of 0-10, with 0=not satisfied and 10=most satisfied, please rate your satisfaction with the education you received on the day of your injection.
2. Would you have preferred a different method of receiving education? If yes, what method?
3. Did the education you received help with the care of your osteoarthritis? If yes, please explain how it helped.
4. PROMIS-10 questionnaire (also administered at baseline, after consent)

**Sample size analysis and statistical analysis plan:** As recommended by Julius, this pilot study will have a sample size of 12 per group (24 total). If deemed feasible, results from this study will be used to design larger, future studies.

Descriptive statistics will be employed for this pilot study. Patient/provider satisfaction results will be summarized as mean with standard deviation or median with 1st and 3rd quartiles. Patient/provider preference results (yes/no) will be presented as counts and percentages. Whether the education helped with the patient's care of OA (yes/no) will also be presented as counts and percentages. PROMIS-10 scores will be summarized as mean with standard deviation or median with 1st and 3rd quartiles. Comparisons between continuous or categorical variables will be assessed using the Student's t-test or Chi-square test, respectively.

1. Julius SA. Sample size of 12 per group rule of thumb for a pilot study. *Pharmaceut Statist.* 2005 Oct;4(4):287-291.

12. Lawrence RC, et al. Estimates of the prevalence of arthritis and other rheumatic conditions in the United States, part II. *Arthritis Rheum*. 2008 Jan;58(1):26-35.

13.

14. Losina E, et al. Lifetime risk and age of diagnosis of symptomatic knee osteoarthritis in the US. *Arthritis Care Res.* 2013 May;65(5).
3. Bastick AN, et al. Defining knee pain trajectories in early symptomatic knee osteoarthritis in primary care: 5-year results from a nationwide prospective cohort study (CHECK). *Br J Gen Pract.* 2016 Jan;66(642):e32-9.
4. Jordan KM, et al. EULAR Recommendations 2003: an evidence-based approach to the management of knee osteoarthritis: report of a task force of the standing committee for international clinical studies including therapeutic trials (ESCISIT). *Ann Rheum Dis.* 2003 Dec;62(12):1145-55.
5. Schrieber L, et al. Patient education. *Best Prac Res Clin Rheum.* 2004;18(4):465-476.
6. Friedman AJ, et al. Effective teaching strategies and methods of delivery for patient education: a systematic review and practice guideline recommendations. *J Cancer Educ.* 2011 Mar;26(1):12-21.
7. Koehn CL, et al. Patient education and self-management of musculoskeletal diseases. *Best Prac Res Clin Rheum.* 2008;22(3):395-405.

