**Sample size analysis and statistical analysis plan:** As recommended by Julious (1), this pilot study will have a sample size of 12 per group (24 total). If deemed feasible, results from this study will be used to design larger, future studies.

Descriptive statistics will be employed for this pilot study. Patient/provider satisfaction results will be summarized as mean with standard deviation or median with 1st and 3rd quartiles.

Patient/provider preference results (yes/no) will be presented as counts and percentages. Whether the education helped with the patient's care of OA (yes/no) will also be presented as counts and percentages. PROMIS-10 scores will be summarized as mean with standard deviation or median with 1st and 3rd quartiles. Comparisons between continuous or categorical variables will be assessed using the Student's t-test or Chi-square test, respectively.

1. Julious SA. Sample size of 12 per group rule of thumb for a pilot study. *Pharmaceut Statist.* 2005 Oct;4(4):287-291.

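### Secondary outcome 3 (quality of education) has no stated scale, and the only item that seems to measure it is yes/no; a 0-10 rating would tell later studies more at almost no cost.

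*Combined protocol and SAP*

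**What the plan says.** - **Outcome.** Secondary outcomes, item 3, reads "Quality of education on post-injection care – assessed at 1 and 3 months post-injection". No scale, score or instrument is given.
- **Item.** Under Study procedures, the third patient question at 1 and 3 months is "Did the education you received help with the care of your osteoarthritis? If yes, please explain how it helped". It is the only patient item that fits outcome 3, although no sentence links the two. The free text is requested only after a 'yes'.
- **Analysis.** Sample size analysis and statistical analysis plan: "Whether the education helped with the patient's care of OA (yes/no) will also be presented as counts and percentages". On testing, the same section says "Comparisons between continuous or categorical variables will be assessed using the Student's t-test or Chi-square test, respectively". It describes no analysis of the free text.
- **Existing 0-10 format.** The first patient question, at the same contacts, uses a 0-10 scale and asks patients to "please rate your satisfaction with the education you received on the day of your injection".
- **Purpose.** "Descriptive statistics will be employed for this pilot study". The size of 12 per group comes from a cited rule of thumb, and the results are meant to inform the design of larger studies.

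The procedures and statistical text appear twice in the document. Both copies read the same on these points.

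**The concern.** Quality is ordinarily a matter of degree, but the item records only whether the education helped at all. Both methods use the same handout, and method 2 adds about five minutes of explanation. If the explanation works, the likely contrast is between some help and more help, which a yes/no answer cannot show.

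What is at stake is mainly planning information. If nearly everyone says 'yes', the pilot yields two proportions close to 100% and no standard deviation for this outcome. A graded answer cannot be recovered after yes/no data have been collected. The planned between-arm comparison also becomes less sensitive, but that matters less in a descriptive pilot.

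**Working it through.** **Plan's own figure.** The sample size is 2 × 12 = 24, from a rule of thumb. No power, effect size, SD or alpha is stated, so there is no power figure to reproduce.

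**Inputs from the documents.** 12 per arm; yes/no item; Chi-square for categorical and Student's t-test for continuous variables (continuity correction or exact version not specified).

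**Assumed inputs.** Two-sided 5%; no dropout; normal latent rating, N(0,1) in method 1 and N(d,1) in method 2, with d = 0.5, 0.8 or 1.0; method 1 'yes' rate p1 from 30% to 90%.

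**Formulas.**
- Threshold for 'yes': c = Φ⁻¹(1 − p1). Method 2 'yes' rate: p2 = Φ(d − c).
- 0-10 rating = round(5.5 + 2 × (latent − c)), capped at 0 and 10, so the latent SD is 2 points.
- Yes/no power: exact sum over the two binomial distributions of outcomes where the uncorrected Pearson Chi-square exceeds 3.84.
- Rating power: pooled t-test on 22 df, simulated with 200,000 trials per setting. As a check without rounding or capping, the noncentral t with parameter d × √(12/2) gives 21.6%, 46.6% and 64.9% for the three values of d.

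**One setting in full.** With p1 = 80% and d = 0.8, c = −0.842 and p2 = Φ(1.642) = 95.0%. Power is 44.0% for the rating and 11.8% for yes/no, a loss of about 32 points.

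**Power, 0-10 rating v yes/no (%).**

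| Method 1 'yes' rate | 0.5 SD | 0.8 SD | 1.0 SD |
|---|---|---|---|
| 30% | 21.2 v 17.7 | 45.9 v 37.4 | 63.9 v 52.8 |
| 40% | 21.4 v 19.1 | 46.0 v 37.2 | 64.1 v 50.7 |
| 50% | 21.3 v 17.9 | 45.7 v 33.3 | 63.7 v 44.8 |
| 60% | 21.2 v 15.1 | 45.7 v 27.6 | 63.4 v 37.3 |
| 70% | 21.0 v 11.9 | 45.0 v 21.2 | 62.7 v 28.0 |
| 80% | 20.8 v 7.6 | 44.0 v 11.8 | 61.2 v 14.3 |
| 90% | 19.8 v 1.7 | 41.2 v 2.1 | 57.2 v 2.2 |

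The smallest loss is about 2 points (0.5 SD, 40%); at 0.5 SD with 30% or 50% it is about 3.5. The largest is 55 points (1.0 SD, 90%). At 'yes' rates of 50% or below, no loss exceeds about 19 points.

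**Test variant.** The exact size of the uncorrected Chi-square at 12 per arm is 6.4% at a 50% 'yes' rate and 1.5% at 90%, so the approximation is poor with sparse cells. With Fisher's exact test or Yates' correction the loss grows. At 0.5 SD and 50% it is 12.9 points against the uncapped t-test, compared with 21.6 − 17.9 = 3.7 for the uncorrected test.

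**Planning information.** If all 12 patients in an arm answer 'yes', the exact 95% CI has lower limit 0.025^(1/12) = 0.735, so it runs from 74% to 100%. In the worked setting, the chance that every method 2 patient says 'yes' is 0.95^12 = 54%.

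**The case against.** - **Power is the wrong yardstick.** Largely right. The main goal is feasibility, the analysis is descriptive, the directional hypothesis concerns satisfaction, and there is no power target. Even the 0-10 item has only about 20-22% power at 0.5 SD and 41-46% at 0.8 SD. What remains is that the statistical section does plan between-arm tests, and that the loss of planning information does not depend on any test.
- **A 0-10 rating of the education already exists.** Satisfaction will supply a mean difference and an SD. But the plan lists it separately from quality of education, and being satisfied differs from being helped with care. The two ratings may well correlate.
- **The 0-10 item can also hit a ceiling.** True. With a 90% method 1 'yes' rate, 53% of method 2 patients would score 10 at 0.8 SD and 61% at 1.0 SD. Observed mean differences shrink to about 1.1 from 1.6 points and 1.35 from 2.0. The rating still carries more information there: 41% v 2% power at 0.8 SD.
- **High 'yes' rates are not documented.** Correct. That most patients will say 'yes' is a plausible consequence of the shared handout, not something the plan states.
- **Stronger readings a reader might infer.** One is that the plan defines a graded outcome and then dichotomises it. It does not: no scale is defined, 'graded' is inferred from the word 'quality', and the link from outcome 3 to question 3 is itself an inference. Another is that only yes/no is collected. Free text is also collected, though its analysis is not described.

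**Conclusion.** The point holds as a low-cost improvement of minor severity. Outcome 3 has no stated scale, and the item that appears to measure it cannot register degrees of help, which is where two arms sharing a handout would be expected to differ. In every setting examined the 0-10 rating had more power. The loss from yes/no was roughly 2 to 55 points for 0.5 to 1.0 SD and method 1 'yes' rates of 30% to 90%, and it was large only when 'yes' rates were high.

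That range rests on an assumed effect size, 'yes' rate, cut-point, SD, alpha and test variant, none of which the documents give. It should not be read as a known power loss in this trial, nor as evidence that the pilot is invalid or too small for its purpose. The main gain from the change is a usable mean difference and SD for later studies.

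**What to change.** 1. In both copies of question 3, ask how much the education helped with care on a 0-10 scale (0 = did not help at all, 10 = helped a great deal). Keep the free-text explanation.
2. State that this item measures secondary outcome 3. The outcome names post-injection care and the item names osteoarthritis care, so the care topic should be made the same in both places.
3. In both copies of the statistical section, summarise the item by arm as mean (SD) or median (quartiles), with the between-arm difference and 95% CI at 1 and 3 months.
4. If a percentage 'helped' is still wanted, derive it from a pre-stated cut (for example, 6 or more) and show it descriptively beside the full distribution.

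**Cost.** One reworded item, one sentence linking it to the outcome, and one revised analysis sentence, with no added visits, patients or staff. The downsides are small: the percentage becomes a derived figure, the rating may correlate with satisfaction, and scores may still cluster near 10.
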